psychiatry, psychology, or behavioral modification. Information on PHQ-9 scores, referrals, patient's uptake (or decline) of prescribed treatments are also captured by our EMRs. Any clinical diagnosis and treatment of depression for those not captured by the screening will also be identified through EMRs. During the glucola visit (22-24 weeks of gestation), all women will be screened for depression a second time using the same screening process as the first prenatal visit.

Women being treated for depression before the screening will be identified (<2%) and analyzed as a separate group.

Depression severity will also be used for stratification (to control for confounding by indication) when conducting head-to-head comparison of treatment effect among various treatment options.

Depression type (with or without other psychiatric comorbidity) will be determined by identifying concurrent psychiatric disorders from KPNC EMRs including organic psychotic conditions, other psychoses, neurotic and personality disorder and other mental disorders. The expected number of women who have depression only and depression with comorbidity during the study period is listed in Figure 2.

Antidepressant use during pregnancy. Antidepressant use, including types, timing, and duration of use, will be ascertained both through the depression screening and EMR (i.e., pharmacy database). The KPNC pharmacy database captures all inpatient and outpatient prescriptions and dispensations. Because of a large financial incentive to obtain medications at KPNC (in most cases, medications are covered with minimal co-payments), the KPNC pharmacy database has been shown to capture 93-98% of prescription medications of varying types. Compliance of taking antidepressants will also be ascertained during interview.

Psychotherapy. KPNC EMR records any psychotherapy patients receive for depression. The information includes the type of therapies (individual or group), sources of the treatment (psychologist, behavioral modification specialist, or psychologist/social worker) and number of sessions attended.

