Cohort C: women who screened positive and used both antidepressants and psychotherapy. This will be a cohort similar to Cohort A and B except that women in this cohort received combination therapies after screening positive. We classify them in a separate cohort to make Cohorts A and B encompass more clearly defined exposures of antidepressants and psychotherapy (pure exposure groups). In addition, this cohort may allow us to examine the potential benefit of combination therapy. Like Cohorts A and B described above, they will be compared to untreated comparator (Cohort D) for Specific Aim 1 and other treatment comparators (Cohort A and B) for Specific Aim 2.

Cohort D: women who screened positive for depression, and did not obtain treatment. Pregnant women whose PHQ-9 score is ≥ 10 at either of two screening visits (the first prenatal visit and glucola visit) or who were diagnosed as having depression by their medical providers, but did not receive any treatment for depression during pregnancy, will be classified into this cohort. Comparison of this cohort to Cohort E (control cohort), a comparator for Specific Aim 3, will allow us to assess whether untreated depression during pregnancy increases fetal risk (i.e., PTD or LBW) without the interference of treatment effect. We can also examine potential dose-response relationships based on the severity of depression (PHQ-9 scores) and duration of depression (persistence of the symptoms in both screening visits vs. at only one of the visits). Importantly, this cohort can be used as a comparator for Cohorts A, B, and C to examine the effect of depression treatment after controlling for underlying depression and severity (untreated comparators).

Cohort E (controls): women who screened negative for depression in both visits and did not receive treatments for depression. This cohort consists of the largest number of pregnant women, those who have neither depression and concurrent psychiatric comorbidity, nor treatment during pregnancy. This cohort will serve as the comparator for determining the effect of untreated depression on fetal risk (i.e., PTD, LBW). It will also serve as a reference check for other

comparisons. For example, does the benefit of a treatment totally eliminate the risk of PTD associated with depression during pregnancy?

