6 ANALYTIC METHODS

6.1 General Approach to Analyses

While all eligible pregnant women will be included in the registry after their pregnancies are identified, the follow-up time for all pregnancy outcomes of interest will start at 20 weeks of gestation because, by definition, PTD and LBW among live births occur after 20 weeks of gestation. All pregnancies ending before 37 completed weeks (259 days) will be considered as failure (PTD). As in our previous studies, we will use the Cox proportional hazards regression model, accommodating delayed entry into the cohort^{76,77}. Birthweight for all newborns will be obtained from EMR and analyses for LBW will utilize logistic regression.

The study design can be characterized as two-stage. Unlike typical applications of two-stage sampling in epidemiologic studies, where the stage-two sample is selected on the basis of both exposure (or exposure surrogate) and outcome (e.g. two-stage case-control sampling), only exposure status will be known at the time of stage-two sampling to keep the nature of a cohort study design. However, study outcomes of interest will eventually be measured on all 88,000 stage-one units, and there is much to be gained by utilizing all available information in estimation of associations of interest (see Sample Size and Statistical Power section).

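### Cohort E's two-screen definition with follow-up from 20 weeks lets births before the second screen count in D but not in E, pushing Aim 3 modestly upward

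*Combined protocol and SAP*

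**What the plan says.** Section 5 (Comparators) gives the detailed cohort definitions. Cohort E is "women who screened negative for depression in both visits and did not receive treatments for depression". Cohort D is untreated women with a PHQ-9 score of 10 or more "at either of two screening visits (the first prenatal visit and glucola visit) or who were diagnosed as having depression by their medical providers". Section 3.1.3 fixes the second screen: "During the glucola visit (22-24 weeks of gestation), all women will be screened for depression a second time".

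Section 6.1 says that "the follow-up time for all pregnancy outcomes of interest will start at 20 weeks of gestation" and counts any pregnancy that ends short of 37 completed weeks as a preterm delivery (PTD). For PTD, "we will use the Cox proportional hazards regression model, accommodating delayed entry into the cohort"; the entry time is not defined by cohort or by screening date. For low birthweight (LBW), "analyses for LBW will utilize logistic regression".

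Section 5 settles cohort membership at the end of pregnancy. Section 4.1.2 excludes women who meet none of the nine definitions. The opening summary, Section 2 and Section 4.1.1 describe E only as screen negative and untreated, without saying how many screens are needed.

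**The concern.** Membership of E depends on something that happens after follow-up has begun. A woman can be in E only if she is still pregnant at the second screen, so E has no events between 20 weeks and that visit. Women in D who were positive at the first screen are at risk, and counted, throughout the same weeks. This is immortal time in the reference group.

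Aim 3 rests on this contrast. Its hazard ratio is the plan's estimate of the fetal risk of leaving depression untreated, which Section B.3 offers to women and clinicians for treatment decisions. Confounder adjustment, propensity scores and instrumental variables cannot put back women whom the definition has removed.

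**Working it through.** **1. Two women side by side.** Both are untreated, have no clinical diagnosis, and deliver at 21 weeks, before the second screen.

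- *Negative at the first screen.* She has no second negative screen, so she fails the Section 5 definition of E. She is not in A-D. Section 4.1.2 excludes her.
- *Positive at the first screen.* She meets the Section 5 definition of D. Her delivery falls after 20 weeks and before 37, so it is a PTD event.

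**2. The plan's own figures.** Section 6.2.2 gives minimum detectable PTD hazard ratios (HR) of 1.69-1.83 for 400 per group, and 1.32-1.38 for an effective 1,600 per group (PTD rates 11% and 8%). Take the Schoenfeld formula with 1:1 groups, two-sided alpha 0.05, 80% power and the rate r read as the reference-group rate, and solve

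0.25 × n[r + 1 − (1 − r)^HR] × (ln HR)² = (1.960 + 0.842)²

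This gives 1.685 and 1.816 for n = 400, and 1.321 and 1.380 for n = 1,600. The stated figures reproduce, so they are a fair yardstick.

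**3. Size of the bias when the true HR is 1.** Let p be the PTD risk from 20 weeks (8-11%, Section 6.2.2). Let x be the proportion of pregnancies ending between 20 weeks and the second screen. The documents do not give x; I assume 0.2-0.5%. E loses all of x, so its observed risk is about p − x. If all of D qualifies at the first screen, D keeps p. If half does, the other half also cannot have had an early event, and D averages p − 0.5x. The documents do not give that share either.

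| p | x | all of D early: p/(p − x) | half of D early: (p − 0.5x)/(p − x) |
|---|---|---|---|
| 0.11 | 0.002 | 1.019 | 1.009 |
| 0.08 | 0.002 | 1.026 | 1.013 |
| 0.11 | 0.005 | 1.048 | 1.024 |
| 0.08 | 0.005 | 1.067 | 1.033 |

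On the cumulative-hazard scale, ln(1 − p)/[ln(1 − p) − ln(1 − x)] gives 1.017 and 1.064 at the extremes of the third column, so the simple ratio is adequate.

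**4. Check by simulation.** Inputs, all assumed apart from the midpoint PTD rate: 10,000 women in D, 40,000 in E, PTD 9.5%, second screen at 24 weeks, true HR 1, 60 runs per scenario. The share of PTD falling in the window was 1%, 3%, 5% or 10%; the table above corresponds to x/p from 0.002/0.11 = 1.8% to 0.005/0.08 = 6.3%.

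- Everyone starts at 20 weeks, all of D early: HR 1.00, 1.03, 1.06, 1.11.
- Everyone starts at 20 weeks, half of D early: HR 1.00, 1.02, 1.03, 1.07.
- Both cohorts start at the second screen: 0.997-1.002 in every scenario.
- Each woman enters when her cohort status is known: 0.992-1.006.

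**5. LBW.** The same women are missing from E, and a logistic model has no entry time through which to correct for it. I give no separate size, because it depends on how many births in the window are live births.

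**The case against.** **The formal criterion for E may be the looser one.** Section 4.1.1 asks only that a woman be screen negative and untreated, and Section 7.1.1 says all eligible women will be classified. Under that wording the woman delivering at 21 weeks belongs in E. This stands as a limit: the bias follows from the Section 5 definition, and a reader who infers that E is event-free under every statement in the plan goes too far. The plan does not say which definition governs.

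**Delayed entry is already planned.** If it means entry when cohort status is known, the Cox bias disappears (step 4). But Section 6.1 states a 20-week start and does not link entry to the second screen. LBW would remain affected in any case.

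**D has event-free time too.** Women positive only at the second screen cannot have had an earlier event. This is correct, and it roughly halves the factor if half of D qualifies late.

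**The bias is small against planned precision.** A reader might infer that it is large because D and E are the biggest cohorts. Section 5 says that only of E. The detectable HRs of 1.32 and 1.38 imply standard errors of the log HR of ln 1.32/2.802 = 0.099 and ln 1.38/2.802 = 0.115. The bias is then at most ln 1.067/0.115 = 0.6 standard errors, and at most ln 1.033/0.115 = 0.3 if half of D qualifies late. It could not by itself create an effect of the planned size.

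**Model diagnostics are planned.** Section 6.1 tests proportional hazards, and this extends to Aim 3. But the tests run in the stage-two sample, where 400 women in D would give only about 400 × 0.002 = 0.8 to 400 × 0.005 = 2 early events.

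**Cohort status might seem to need freezing at 24 weeks.** That would go against Section 5, which settles membership at the end of pregnancy, and would change what is compared. It is not needed to remove the bias described here.

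**Conclusion.** The point holds in a conditional form. Under the Section 5 definitions and a 20-week start, the D versus E comparison is biased upward for PTD and LBW. The looser definitions of E and the undefined delayed entry mean that the documents do not settle whether the analysis would be run that way, so the first need is to reconcile them.

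The size is modest: an HR factor of about 1.02-1.07 if all of D qualifies at the first screen and about 1.01-1.03 if half does, assuming 0.2-0.5% of pregnancies end in the window. Neither input is in the documents. The factor is below the planned detectable HRs of 1.32-1.83. It is systematic, however, so the 88,000 stage-one women narrow the interval around it without reducing it. It should be corrected; it does not undermine the study.

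**What to change.** 1. Reconcile the definitions of Cohort E in the summary and Sections 2, 4.1.1 and 5. State how a woman is classified who misses the second screen or delivers before it.
2. For Aim 3, set Cox entry for both D and E at the second screen (or 24 completed weeks), using the delayed entry already in Section 6.1.
3. Restrict the Aim 3 logistic model for LBW to women still pregnant at that same point.
4. Report births from 20 weeks to that point separately, by first-screen result.

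The cost is a few sentences, a changed entry time and one descriptive table. No new data are needed, since the records already hold PHQ-9 scores and delivery dates. The downside is that the few births before 24 weeks leave the Aim 3 models, which is why the fourth item matters.

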- Aim 3.** Do women with untreated depression have a higher fetal risk than women without depression? (Cohort D vs. E).
- Aim 4.** Does the treatment effectiveness differ between women with depression only and women with depression and other comorbidity?

Exploratory analyses will be conducted to examine whether treatment effectiveness (Aims 1 & 2) is impacted by baseline depression severity. The aims will be refined with continued input from stakeholders. This will be the first large scale comparative effectiveness study to answer pressing clinical questions with an innovative and efficient two-stage design.

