3.1 Study Design

3.1.1 Overview of the Study Design and Approaches

The proposed study will be a population-based prospective cohort study with an efficient two-stage design. This study design is uniquely suited for the KPNC available infrastructure, an advanced and comprehensive EMR system and universal peripartum depression screening program. Given that recalling depression during pregnancy in the presence of adverse pregnancy outcomes (PTD or LBW) is likely biased (recall bias), retrospective study designs like case-control studies are not appropriate for the objectives of the proposed study. Thus, a prospective cohort study design obtaining information on depression and its treatment during pregnancy before pregnancy outcomes is the only appropriate study design for addressing the Specific Aims of the proposed study. In addition, KPNC's unique infrastructure allows for an efficient two-stage prospective cohort study. The KPNC comprehensive EMR which captures the PHQ-9 scores for participants of the universal depression screening allows us to identify information on depression and its treatment status for 88,000 pregnant women expected to be screened. KPNC EMR will also allow us to ascertain pregnancy outcomes, PTD and LBW; thus, we will have information on exposures (depression and its treatment) and outcomes (PTD and LBW) for all 88,000 pregnant women during the study period to form 4 comparison cohorts within each depression type (with or without comorbidity) and one control cohort (a total of nine cohorts). While it is not practical to interview 88,000 women, contacting and interviewing 3,600 (400 from each cohort) in the stage-two sample will allow us to obtain information on confounders. Information on underlying depression severity at baseline allows us to control for confounding by indication and to examine comparative effectiveness of treatment options among women with similar severity of underlying depression. Other psychiatric disorders captured by KPNC EMR will allow us to examine treatment effectiveness separately for two different types of depression. Combining information from both stage-one and stage-two populations allow us to examine the Specific Aims using an appropriate study design (prospective cohort study) with an efficient approach (two-stage design). KPNC's infrastructure makes this unique combination of study designs possible.

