4.1 Study Population

4.1.1 Inclusion Criteria

- 1) Females \geq age 18
- 2) Kaiser members
- 3) Pregnant beyond 20 weeks of gestation during the recruitment period
- 4) Meeting the definition of one of the following nine cohorts:

Cohort A (depression only): pregnant women who are depressed and use only antidepressants

Cohort A (depression with comorbidity): pregnant women who are depressed and use only antidepressants

Cohort B (depression only): pregnant women who are depressed and receive psychotherapy only

Cohort B (depression with comorbidity): pregnant women who are depressed and receive psychotherapy only

Cohort C (depression only): pregnant women who are depressed and receive antidepressants and psychotherapy

Cohort C (depression with comorbidity): pregnant women who are depressed and receive antidepressants and psychotherapy

Cohort D (depression only): pregnant women who are depressed and receive no treatment

Cohort D (depression with comorbidity): pregnant women who are depressed and receive no treatment

Cohort E: pregnant women who are not depressed (screen negative) and receive no treatment

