Regression parameter estimates and associated standard errors will be obtained via semiparametric maximum likelihood⁷⁸, utilizing exposure and outcome measurements on all 88,000 stage-one units in addition to confounder/effect modifier measurements on the subset sample at stage-two (N=3,600). Scott and Wild presented a unified method for fitting arbitrary regression models to a large class of missing data and/or response selective sampling problems. These applications are generally characterized as: 1) a set of easily-obtainable variables is measured on a sample of N individuals; one or more of these variables are to be used as explanatory in the regression model (e.g. depression and treatment status), or are informative surrogates for “expensive” variables to be measured on a subsample; 2) the response variable is obtained for all N individuals (e.g. PTD, LBW); and, 3) a set of “expensive” explanatory variables (e.g. potential confounders/effect modifiers) are measured on a subsample. Software (R language) has been developed and available from the authors, with functions for various regression models including binary regression, linear regression for continuous response, and clustered binary data. The associated software documentation provides details on key parts of the system enabling users to implement new regression models (e.g. Cox). We will utilize logistic and Cox regression to address the study aims, as described below.

Each set of analyses addressing Aims 1, 2 and 3, outlined below, will be conducted in samples of women with and without other psychiatric comorbidities (Aim 4).

Aim 1. Treatment effect compared to untreated depression (Cohort A, B & C vs. Cohort D)

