Aim 3. Risk of PTD & LBW for untreated depression (Cohort D vs. E)

Cox proportional hazards regression will be used to obtain point and interval estimates of the hazard ratio for PTD associated with untreated depression, vs. no depression, with adjustment for potential confounders, as described above. Parameter estimation, the approach to inclusion of potential confounders and model diagnostics are as described above for Aim 1 analyses.

To evaluate potential dose-response relationships, we will examine the strength of the association between PTD and severity of depressive symptoms. Severity will be based on results of the KPNC universal screening and clinical diagnosis of depression from the KPNC EMR. Those with a clinical diagnosis of depression will be considered to be the most severe cases followed by those who screened positive with PHQ-9 higher scores (e.g., > 20). Those who screened positive, but with lower PHQ-9 scores (10-19) will be considered to have moderate depression. The effect of severity will also be examined in terms of duration.

Analyses of LBW as the outcome will parallel those described above for PTD, but logistic regression techniques will be used rather than the Cox model.

Aim 4. Difference in treatment effectiveness by depression type (with and without comorbidity)

Analyses of Aims 1, 2 and 3, will be initially stratified by depression type, with or without other psychiatric comorbidity (yes/no). Heterogeneity in treatment effectiveness by depression type will be assessed by inclusion of appropriate cross-product (interaction) terms in regression models outlined above, using a likelihood ratio test. If there is evidence of heterogeneity, point and interval estimates of relative hazards/odds ratios of interest by comorbidity status (yes/no), adjusted for confounders, will be obtained via linear combination of regression parameter estimates (main effect and interaction terms, as appropriate).

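### Aim 3 is stratified by psychiatric comorbidity but Cohort E is not clearly split; if E is comorbidity-free, the comorbid-stratum result is a joint association, not the effect of untreated depression

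*Combined protocol and SAP*

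**What the plan says.** - **The question.** Aim 3 in section 2 asks: "Do women with untreated depression have a higher fetal risk than women without depression". Section 6.1, Aim 3, reports the answer as the "hazard ratio for PTD associated with untreated depression, vs. no depression", with low birthweight handled in parallel by logistic regression.
- **Stratification.** Section 6.1 says that each set of analyses for Aims 1, 2 and 3 "will be conducted in samples of women with and without other psychiatric comorbidities (Aim 4"). Under Aim 4 it repeats: "Analyses of Aims 1, 2 and 3, will be initially stratified by depression type, with or without other psychiatric comorbidity (yes/no").
- **Cohort structure.** Section 3.1.1 plans "4 comparison cohorts within each depression type (with or without comorbidity) and one control cohort (a total of nine cohorts"), that is 4 × 2 + 1 = 9. Sections 4.1.1 and 5 likewise have one E.
- **Who is in E.** Section 4.1.1 has "Cohort E: pregnant women who are not depressed (screen negative) and receive no treatment", with no comorbidity condition; the abstract and section 2 agree. Section 5 opens its Cohort E paragraph in similar terms, then describes the members as "those who have neither depression and concurrent psychiatric comorbidity, nor treatment during pregnancy".
- **What E is for.** Section 5: "This cohort will serve as the comparator for determining the effect of untreated depression on fetal risk".

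No section names the reference group for the with-comorbidity stratum of Aim 3, or says that this contrast should be read as a joint association.

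**The concern.** In Aims 1 and 2 both sides of every comparison are divided by comorbidity, so each stratum compares like with like. In Aim 3 only D is divided. If E contains no comorbid women, everyone in D (with comorbidity) has both conditions and everyone in E has neither. Any effect of the other psychiatric disorder on preterm delivery is then counted as an effect of untreated depression.

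What is at stake is the Aim 3 conclusion in one of its two strata. A raised hazard ratio there could come wholly from the comorbidity, and the plan's wording would still attribute it to leaving depression untreated.

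**Working it through.** **1. The plan's own figure.** Section 6.2.2 gives minimum detectable hazard ratios of 1.69 to 1.83 for a pairwise contrast of 400 vs 400 at preterm rates of 11% and 8% (two-sided 0.05, power 0.80). Taking the stated rate r as the reference-group rate:

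- events d = 400 × [r + 1 − (1 − r)^HR]
- power = Φ(ln HR × √d / 2 − 1.96)
- r = 0.11, HR = 1.69: d = 115.5, power = 0.805
- r = 0.08, HR = 1.83: d = 88.6, power = 0.812

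Solving for 80% power gives 1.685 and 1.816. The plan's effective sample size of 3,200 gives 1.321 and 1.380, against its stated 1.32 to 1.38. The sample-size arithmetic for D vs E therefore stands. The question is what the contrast measures.

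**2. Section 5 reading: E has no comorbidity.**

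| Group | Depression | Comorbidity |
|---|---|---|
| E | 0 | 0 |
| D, depression only | 1 | 0 |
| D, with comorbidity | 1 | 1 |
| (no such group) | 0 | 1 |

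In D (with comorbidity) vs E the depression and comorbidity columns are identical, so a model holding both cannot be fitted. The estimated quantity is

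HR(D with comorbidity vs E) = HR(depression) × HR(comorbidity) × any interaction.

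Pooling all three groups does not rescue the stratum. Depression, comorbidity and their interaction make a four-column design (with intercept) of rank 3. If the interaction is assumed away, the depression effect is simply the one from D (depression only) vs E.

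**3. Size on that reading.** The comorbidity hazard ratio h is an assumption. With HR(depression) = 1 the labelled result equals h. Using the formula above with r = 9.5% (the midpoint used in section 6.2.2), the chance of declaring an untreated-depression effect is:

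| h | 400 per group | 1,600 per group (effective N 3,200) |
|---|---|---|
| 1.2 | d = 83.2, 13% | d = 332.6, 38% |
| 1.5 | d = 93.6, 50% | d = 374.5, 97.5% |

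More data makes the misattribution more certain.

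**4. Section 4.1.1 reading: E includes comorbid women.** Let p be the comorbid share of E, assumed 5% to 15% because the documents do not give it. With no depression effect:

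- *E not split, no adjustment:* HR ≈ h / (1 + p(h − 1)). For h = 1.2: 1.2/1.010 = 1.188 and 1.2/1.030 = 1.165. For h = 1.5: 1.5/1.025 = 1.463 and 1.5/1.075 = 1.395. The result is about 1.17 to 1.46, so a mixed E dilutes the problem only slightly.
- *E split:* D (with comorbidity) is compared with comorbid E women, and HR = h/h = 1.00. The mislabelling is gone.

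**5. Can E be split?** Section 3.1.3 takes other psychiatric disorders, treatment and outcomes from the medical record for all 88,000 screened women, so stage-one data allow it.

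**The case against.** The best defence has three parts.

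*The section 5 clause is ungrammatical.* It could mean that E women do not have depression and comorbidity jointly, and the opening of the same paragraph sets no comorbidity condition. This stands: the comorbidity-free reading is the more natural one, not a certain one.

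*If section 4.1.1 governs, the stratification sentence in section 6.1 can be read as splitting E too.* This also stands, and on that reading nothing is mislabelled. But the nine-cohort structure shows a single E, and the plan never says that E is divided for Aim 3.

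*A common unexposed reference for two exposure subtypes is standard.* Section 1 (A.a.6) treats depression with comorbidity as possibly a different disease entity, and Aim 3 asks only about women without depression. This justifies reporting the contrast as the association of that entity. It does not justify calling the result the effect of untreated depression.

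A reader might infer more than the documents support:

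- *That propensity-score trimming would empty the contrast.* Section 6.1.1 models the probability of receiving one treatment against another or none. D and E are both untreated, and Table 1, as extracted, lists history of mental illness rather than concurrent comorbidity among the potential confounders.
- *That a split E would be too small to use.* Under the assumed shares only 400 × 0.05 = 20 to 400 × 0.15 = 60 interviewed E women would be comorbid. But the planned estimator also uses stage-one data, so a power figure from those few women alone would not describe the plan.
- *That the heterogeneity test in Aim 4 fails.* Sections 2 and 6.1 limit that test to treatment effectiveness. Section 6.2.2 mentions depression alongside treatment, but its example is A vs D.

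**Conclusion.** The point holds in conditional form. Aim 3 is explicitly stratified by comorbidity, E is set up as one cohort, and sections 4.1.1 and 5 describe E differently. If E is comorbidity-free, the comorbid-stratum hazard ratio (and the parallel low-birthweight odds ratio) is a joint association carrying the wrong label, and adjustment within that contrast cannot correct it. With a null depression effect the whole comorbidity hazard ratio is passed through: 1.2 to 1.5 under the assumed values, for which the documents offer no figure. If E includes comorbid women and is actually split, the fault disappears.

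It would be wrong to conclude that Aim 3 as a whole fails. D (depression only) vs a comorbidity-free E is sound. Aims 1 and 2 and their treatment-by-comorbidity tests are untouched. The point should be fixed before analysis because it changes what one stratum may be said to show.

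**What to change.** 1. Reconcile sections 4.1.1 and 5 on whether women with psychiatric comorbidity may belong to E.
2. If E is comorbidity-free, base the Aim 3 conclusion about untreated depression on D (depression only) vs E, and report D (with comorbidity) vs E explicitly as the joint association of depression plus comorbidity.
3. If E includes comorbid women, state that E is split by comorbidity recorded in the medical record, using stage-one data, so that each Aim 3 stratum has a like-for-like reference.
4. Optionally, if E is comorbidity-free, add a supplementary stage-one contrast of D (with comorbidity) against screen-negative, untreated women with comorbidity.

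Items 1 to 3 are text changes. Item 4 needs no new interviews, but the extra record-only group must be written into sections 4.1.1 and 4.1.2, and it would lack the confounders collected only by interview. Settling this before analysis also avoids choosing E's membership once results are known.
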